### **Specific Aims**

- **Aim 1**: To determine whether haloperidol or ziprasidone administered to delirious medical/surgical ICU patients will increase days alive without delirium (measured as delirium/coma-free days [DCFDs]) over a 14-day study period compared with placebo and compared with one another.
- **Aim 2**: To determine whether haloperidol or ziprasidone will improve 30-day, 90-day, and 1-year survival compared with placebo and compared with one another.
- **Aim 3**: To determine whether haloperidol or ziprasidone will reduce ICU length of stay (LOS) (i.e., time to ICU discharge) compared with placebo and compared with one another.
- **Aim 4**: To determine whether haloperidol or ziprasidone will improve long-term neuropsychological outcomes, functional independence, quality of life, and posttraumatic stress disorder symptoms at 3-month and 1-year follow-up compared with placebo and compared with one another.

To complete these Aims, we will consent adult medical and surgical ICU patients (a) on mechanical ventilation or non-invasive positive pressure ventilation, and/or (b) in shock requiring vasopressors. Once delirium occurs, we will randomize a total of 561 delirious patients (187 to the haloperidol group, 187 to the ziprasidone group, and 187 to the placebo group) and follow them for 1 year. In the absence of an indication requiring hold of study drug, patients will receive study drug until delirium has resolved for two days or ICU discharge or 14 days after the day of randomization, whichever occurs first. While tracking **primary** (delirium duration, Aim 1) and **secondary outcomes** (mortality, ICU LOS, and long-term neuropsychological function; Aims 2-4), we will closely monitor safety parameters, including arrhythmias, extrapyramidal symptoms (EPS), neuroleptic malignant syndrome (NMS), and posttraumatic stress disorder (PTSD). **The study sample size was explicitly chosen to ensure adequate power** ( $\geq$  80%) to **detect the effect of antipsychotics in four important subgroups**: age  $\geq$  70 years, high severity of illness (APACHE II  $\geq$  25), presence of severe sepsis at enrollment, and medical vs. surgical ICU patients. We will also conduct hypothesis-generating subgroup analyses of the effect of antipsychotics on delirium in patients with pre-existing cognitive impairment.

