#### 11.0 Statistical Considerations

11.1 Power Analyses and Sample Size Calculations for Delirium (Aim 1). Based on data collected during our BRAIN-ICU Study, we anticipate that patients in the control (placebo) group in MIND-USA will have a mean  $\pm$  SD of 6.8 $\pm$ 5.2 delirium/coma-free days during the 14-day Treatment Period. At a 2-sided significance level of 2.50%, after Bonferonni adjustment for 2 pairwise comparisons (each active treatment will be compared to placebo), a trial of 187 patients per treatment group (total N=561) will have 92% analytical power to detect a 2-day improvement in delirium/coma-free days. Importantly, this sample size will also provide 80% power to detect a 2.5-day improvement in DCFDs within 4 subgroups expected to be ~45% (N=252) of the study population: severe sepsis, age  $\geq$  65 years, high illness severity (APACHE II  $\geq$  25), and medical vs. surgical patients. We will also conduct a hypothesis-generating subgroup analysis for patients enrolled with preexisting cognitive impairment (~25% of study population, N=140).

MIND-USA Protocol Version: 1.15 Confidential Protocol Date: June 22, 2016 34 of 51

- 11.2 Power analyses for Mortality and ICU LOS (Aims 2 and 3). Assuming 40% one-year mortality in the control (placebo) group, this study will have 80% power to detect a 14% absolute difference in one-year mortality at a 2-sided significance level of 2.50% (if control mortality is 50%, study has 80% power to detect 15% difference). For ICU length of stay (LOS), this study will have 80% power to detect a 2.43-day (29%) difference at a 2-sided significance level of 2.50% assuming an 8.2±7.6 day ICU LOS in controls.
- 11.3 Power Analyses for Long-Term Cognitive Impairment (Aim 4). We expect to follow ≥ 80% of survivors for evaluation of LTCI. Based on the expected mortality rates (see above), we expect an overall 31% mortality across all 3 groups and plan to test 310 (=561x0.69x0.80) patients for LTCI at 12 months. Analysis for this aim will use multivariable linear regression to account for potential confounders introduced by imbalances in groups created by death and loss to follow-up. With 310 patients, we will able to include independent variables with up to 21 degrees of freedom. The proposed study will have adequate—indeed abundant—ability to assess the independent effect of the intervention on cognitive impairment while controlling for confounders.

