Regarding the analyses of all *a priori*-defined secondary outcomes described herein, no adjustments will be made for multiple comparisons in keeping with authoritative recommendations on this topic  and standard practice when analyzing multiple, prospectively defined outcomes in a clinical trial. As described in our proposal, each comparison made will be hypothesis-driven and based upon biological plausibility rather than exploratory in nature.

11.5 Interim Analysis. To ensure protocol compliance and safety within the MIND-USA study, we will conduct interim analyses that will allow early presentation of outcomes to the DSMB (see section 9.3). In addition to the final analysis of 561 patients, two interim analyses are planned at 100 patients and 300 patients randomized; these interim analyses will compare 90-day survival in the blinded treatment groups.

Using a modified Haybittle-Peto method, the MIND-USA Study should be terminated or modified (e.g., one group dropped) if the p value for the global test, which simultaneously compares the three treatment groups, is less than 0.0001 at any of the two interim analyses. If the trial continues to completion (N=561 randomized), a p value <0.0498 for the global test will be considered statistically significant to account for the two planned interim analyses. The DSMB will be provided data showing the effect size (relative risk) in order to put the p-values into clinical perspective.

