2.2 Objectives

The MIND-USA study is a multicenter, double-blind, randomized, placebo-controlled trial investigating the effects of intravenously (IV) administered typical and atypical antipsychotics (haloperidol and ziprasidone) on delirium in critically ill patients. The study evaluates the following aims:

- Aim 1: To determine whether haloperidol or ziprasidone administered to delirious medical/surgical ICU patients will increase days alive without delirium and coma (measured as delirium/coma-free days [DCFDs]) over a 14-day study period compared with placebo.
- **Aim 2:** To determine whether haloperidol or ziprasidone will improve 30-day, 90-day, and 1-year survival compared with placebo.
- **Aim 3:** To determine whether haloperidol or ziprasidone will reduce ICU length of stay (LOS) (i.e., time to ICU discharge) compared with placebo.
- Aim 4: To determine whether haloperidol or ziprasidone will improve long-term neuropsychological outcomes, functional independence, quality of life, and post-traumatic stress disorder symptoms at 3-month and 1-year follow-up compared with placebo.

3. Study Methods

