3.3 Power and Sample Size (as was written in the grant)

Power Analyses and Sample Size Calculations for Delirium (Aim 1). Based on data collected during our BRAIN-ICU Study, we anticipate that patients in the control (placebo) group in MIND-USA will have a mean ± SD of 6.8±5.2 delirium/coma-free days during the 14-day Treatment Period. At a 2-sided significance level of 2.50%, after Bonferroni adjustment for 2 pairwise comparisons (each active treatment will be compared to placebo), a trial of 187 patients per treatment group (total N=561) will have 92% analytical power to detect a 2-day improvement in delirium/coma-free days. Importantly, this sample size will also provide 80% power to detect a 2.5-day improvement in DCFDs within 4 subgroups expected to be ~45% (N=252) of the study population: severe sepsis, age ≥65 years, high illness severity (APACHE II ≥25), and medical vs. surgical patients. We will also conduct a hypothesis-generating subgroup analysis for patients enrolled with preexisting cognitive impairment (~25% of study population, N=140).

Power Analyses for Mortality and ICU LOS (Aims 2 and 3). Assuming 40% one-year mortality in the control (placebo) group, this study will have 80% power to detect a 13% absolute difference in one-year mortality at a 2-sided significance level of 1.67% (if control mortality is 50%, study has 80% power to detect 14% difference). For ICU length of stay (LOS), this study will have 80% power to detect a 2-day (24%) difference at a 2-sided significance level of 1.67% assuming an 8.2±7.6 day ICU LOS in controls.

Timing of Final Analysis

In-Hospital Database Cleaning & Lock Procedures

MIND-USA uses the REDCap electronic data capture platform for data collection. Upon completion of the in-hospital portion of the MIND-USA study, the following procedures will be followed and documented within the Database Cleaning & Lock SOP:

- 1. VCC will work with site coordinators to address all data issues revealed by ongoing data cleaning. This process will continue until all issues have been addressed.
- Upon completion of in-hospital data cleaning, the REDCap database MIND-USA Study: Exclusion Log will be locked in the following way:
 - a. Initially all users with current "view and edit" user privileges will be moved to "read only" user privileges.
 - b. After the window closes for sites to export their data the database will be permanently moved to inactive status (meaning that no data can be changed).

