- 3. Upon completion of in-hospital data cleaning, the REDCap database **MIND-USA Study: In-Hospital Database** will be locked in the following way:
 - a. Initially all study site personnel will be restricted to "read-only" user access for the entire database. VCC Project Managers and the Follow-Up Team will be restricted to read-only access for all fields except those needed for patient contact, reconsenting, DNA permissions, notes to file and event reporting, and tracking dates of death and study withdrawal. All fields not needed by these teams will be restricted to read only by use of the @readonly action tags. The follow-up team will continue to be blinded (via restricted access) to all information about the hospital course, as has been the case throughout the study.

	VCC Project Managers	Follow-Up Team
Dates Tracking Form - all variables made read-only (using action tag @readonly) to all users except variables pertaining to consenting, death and study withdrawal	View and Edit	View and Edit
Contact Form - all fields	Read Only	View and Edit
NTF - all fields	View and Edit	View and Edit
Adverse Events - all fields	View and Edit	View and Edit
DNA Log - all fields	View and Edit	No Access
All other forms/fields	Read Only	No Access

- b. During the remaining Follow-Up period, the sites will be given a window for downloading their data for local storage.
- c. Once 12-month follow-up is completed, we will conduct final data cleans on the updated information and then permanently move the entire database to inactive status, meaning that no data can be changed unless serious errors are noted.

A log of all steps in this process will be maintained in the Database Cleaning & Lock SOP.

4. Statistical Principles

Statistical analysis will be conducted in accordance to the plan outlined in this SAP. Statistical analysis will abide by these general statistical principles below.

Confidence Intervals and P-Values

Level of statistical significance will be set at 5% (with multiple comparisons adjustments for the primary outcome, as noted below). All tests will be two-sided. 95% confidence intervals will be reported along with all effect estimates. Presentation of results will emphasize clinical significance, effect sizes and confidence intervals, over statistical significance.

Modeling Principles

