Whenever possible (based on variable distribution), we will not assume linear associations between covariates and outcomes; rather, nonlinear associations between continuous variables and outcomes will be permitted by inclusion of restricted cubic splines with 3 knots. To account for correlation among patients within a given site, we will adjust standard errors using Huber-White sandwich estimation.

Multiple Comparisons

For the primary outcome (DCFDs), multiple comparisons will be conducted at a 2.5% level if the overall test of association is significant at a 5% level. Regarding the analyses of all *a priori*-defined secondary outcomes described herein, no adjustments will be made for multiple comparisons, in keeping with authoritative recommendations on this topic and standard practice when analyzing multiple, prospectively defined outcomes in a clinical trial. As described in our proposal, each comparison made will be hypothesis-driven and based upon biological plausibility rather than hypothesis-generating in nature.

Missing Data

Individual Variables

Missing data for individual variables will be imputed using clinical imputation rules when appropriate; details on these rules are noted in the Definitions and Derived Variables section. This section also describes the imputation process for summary variables for mental status (eg, days alive and free of delirium and coma), which may involve *partially* missing data.

Missingness when Modeling

In adjusted analyses, model-based multiple imputation strategies will be used (using R's mice library) if >5% of any covariates are missing. In all cases, decisions and processes will be documented both in data management and analysis code and in statistical reports.

Adherence to the Intervention and Protocol Noncompliance

Definition & assessment of adherence to the intervention

All analysis will be conducted based on the intention to treat principle. Subjects will be considered to have the treatment they were randomized to regardless of withdrawal from treatment or extent of exposure.

Presentation of adherence to intervention

We will describe, within each treatment group, the following:

- Patient level:
 - How many randomized patients received >=1 dose of study treatment
 - Days each randomized patient received study treatment
 - Doses of study treatment each randomized patient received, along with average daily dose

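### SAP 3.3 claims 80% power for one-year mortality and ICU stay at two-sided 1.67%, but 187 per arm gives about 56% to 63%; no planned test uses 1.67%, and the figures conflict with protocol 11.2

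*SAP*

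**What the plan says.** SAP section 3.3, whose heading presents the text as taken from the grant, gives 187 patients per arm (561 in total). For Aim 2, with 40% one-year mortality on placebo, it states that "this study will have 80% power to detect a 13% absolute difference in one-year mortality at a 2-sided significance level of 1.67" percent, and it adds 14 points if control mortality is 50%. For Aim 3, with ICU stay of 8.2 days (SD 7.6), it states that "this study will have 80% power to detect a 2-day (24%) difference at a 2-sided significance level of 1.67" percent.

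Protocol section 11.2, with the same sample size, control rates and SD, states that "this study will have 80% power to detect a 14% absolute difference in one-year mortality at a 2-sided significance level of 2.50" percent, with 15 points at 50% control mortality and 2.43 days for ICU stay.

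On the level actually used, SAP section 4 says "Level of statistical significance will be set at 5% (with multiple comparisons adjustments for the primary outcome, as noted below", and for secondary outcomes "no adjustments will be made for multiple comparisons, in keeping with authoritative recommendations on this topic". Protocol 11.4 takes the same position: "no adjustments will be made for multiple comparisons in keeping with authoritative recommendations on this topic".

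**The concern.** For a fixed sample size, control rate, SD and power, a stricter significance level always makes the smallest detectable difference larger. The SAP pairs smaller differences than the protocol (13 against 14 points, 14 against 15 points, 2 against 2.43 days) with a stricter level (1.67% against 2.50%) and the same 80%. Both sets cannot hold, whatever formula is preferred.

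Survival and ICU stay are Aims 2 and 3. A reader who relies on the SAP's 80% to interpret a null result on either would credit the trial with more power than it has, and the two documents would give that reader different answers.

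**Working it through.** **Inputs.** n = 187 per arm with 1:1:1 allocation (SAP 3.2 and 3.3), so each comparison with placebo is 187 against 187. Mortality effects: 40% vs 27% and 50% vs 36% (SAP); 40% vs 26% and 50% vs 35% (protocol). ICU stay: SD 7.6, difference 2 days (SAP) or 2.43 days (protocol). Two-sided critical values z: 2.393 at 1.67%, 2.241 at 2.5%, 1.960 at 5%. Neither document states a dropout allowance for these calculations, so none is applied.

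**Step 1: the method reproduces figures the documents state.**
- Aim 1: SE = 5.2 × √(2/187) = 0.538, and 2/0.538 = 3.719. Power = Φ(3.719 − 2.241) = 93.0% (noncentral t 92.9%), against the stated 92%.
- Protocol ICU stay: SE = 7.6 × √(2/187) = 0.786, and 2.43/0.786 = 3.092. Power at 2.5% = Φ(3.092 − 2.241) = 80.2% (noncentral t 80.0%), against the stated 80%.

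**Step 2: the SAP's three claims at 1.67%.** For proportions, power = Φ[(|p1 − p2| − z·s0)/s1], with s0 = √(2p̄(1 − p̄)/n) and s1 = √([p1(1 − p1) + p2(1 − p2)]/n).
- 40% vs 27%: s0 = 0.0488, s1 = 0.0484; (0.13 − 2.393 × 0.0488)/0.0484 = 0.273, so power is 60.7%.
- 50% vs 36%: s0 = 0.0512, s1 = 0.0507; (0.14 − 2.393 × 0.0512)/0.0507 = 0.345, so power is 63.5%.
- 2 days: 2/0.786 = 2.545; Φ(2.545 − 2.393) = 56.0% (noncentral t 55.6%).

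Reaching 80% at 1.67% would take about 275, 261 and 303 per arm.

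**Step 3: alternative readings at 1.67%.** For the two mortality effects:
- unpooled variance: 61.6% and 64.4%
- arcsine: 61.1% and 63.7%
- log-rank (Schoenfeld): 62.5% and 65.5%
- continuity correction: 56.4% and 59.5%

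Reading 13 points as an increase gives 55.1%. A one-sided 1.67% gives 70.6%, 73.0% and 66.2% for the three effects. Pooling both drugs (187 vs 374) gives 76.4%, 78.4% and 70.7%. None reproduces all three claims.

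**Step 4: the same effects at the other levels** (pooled two-proportion formula; noncentral t for days).

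| Effect | 1.67% | 2.5% | 5% |
|---|---|---|---|
| SAP: 40% vs 27% | 60.7% | 66.5% | 76.1% |
| SAP: 50% vs 36% | 63.5% | 69.1% | 78.3% |
| SAP: 2 days | 55.6% | 61.6% | 71.8% |
| Protocol: 40% vs 26% | 68.8% | 74.1% | 82.4% |
| Protocol: 50% vs 35% | 70.8% | 75.8% | 83.8% |
| Protocol: 2.43 days | 75.4% | 80.0% | 86.9% |

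At 5%, the SAP effects would need about 206, 196 and 228 per arm for 80%.

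**Step 5: differences that do have 80% power with 187 per arm.**

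| Level | Mortality from 40% | Mortality from 50% | ICU stay |
|---|---|---|---|
| 1.67% | 15.6 points | 16.4 points | 2.54 days |
| 2.5% | 14.9 points | 15.7 points | 2.43 days |
| 5% | 13.6 points | 14.3 points | 2.2 days |

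**Step 6: where 1.67% could come from.** 5%/3 = 1.67%, a split over three pairwise comparisons. The protocol's Aim 2 has three: "To determine whether haloperidol or ziprasidone will improve 30-day, 90-day, and 1-year survival compared with placebo and compared with one another". The SAP's Aim 2 has two: "To determine whether haloperidol or ziprasidone will improve 30-day, 90-day, and 1-year survival compared with placebo". Aim 3 differs between the documents in the same way. The levels the documents do use are 5% in general, 2.5% for the pairwise tests of the primary outcome (SAP section 4), and 0.0001 and 0.0498 for the global test at the interim and final analyses (protocol 11.5). None is 1.67%.

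**The case against.** The strongest reply has four parts.

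- **Labelled as grant text.** The heading gives its origin, and the SAP was written after randomization, so the paragraph is probably left over from an earlier three-comparison scheme. That is plausible. But the SAP offers no caveat and no replacement figure, and its own Aim 1 paragraph already uses 2.50% for two comparisons.
- **The planned tests are not these formulas.** Mortality is analysed by log-rank and Cox regression, and ICU stay as time to discharge with death as a competing risk. This is fair, but the effect is small for mortality. At 5% the log-rank approximation gives 77% and 80% for the SAP's effects, with detectable differences of about 13.4 and 14.0 points. A rough three-group log-rank approximation gives about 76% to 82% and 80% to 84%, depending on whether one or both drugs work. For ICU stay, assuming exponential times and 85% to 100% discharged, 2 days has about 70% to 77% power at 5%.
- **Adjusted analyses are primary and may add power.** This is true, but neither document quantifies the gain, so it cannot support a stated 80%.
- **Nothing depends on the paragraph.** The sample size rests on delirium/coma-free days, and the SAP emphasises effect sizes and intervals. This limits the consequence but does not make the figure correct.

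What stands is that the overstatement on mortality at 5% is modest, and that the replacement figures match the planned tests in level, not in test statistic. None of this rescues 80% at 1.67% or removes the conflict with protocol 11.2.

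**Conclusion.** The concern holds. At the stated 1.67%, power is overstated by about 16 to 24 points (60.7%, 63.5% and 55.6% against 80%). At the 5% used for secondary outcomes, it is overstated by about 2 to 8 points under the simple formulas, and by about 3 points or less for mortality under log-rank. The 1.67% matches no analysis in either document.

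Protocol 11.2 is sound for ICU stay under a normal-means model. Its mortality figures give about 74% and 76% at 2.5% (log-rank 76% and 78%), so copying them into the SAP would not cure the problem; they exceed 80% only at 5%.

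These results assume 187 per arm, no loss to follow-up, a fall in mortality, and SD 7.6 in both arms. Loss to follow-up would lower power further. The paragraph should be corrected, but the trial's size and its Aim 1 power are not in question.

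**What to change.** Replace the Aims 2 and 3 paragraph in SAP 3.3, remove 1.67%, and state one significance level with the same figures in SAP 3.3 and protocol 11.2. Suggested text, at the level planned for secondary outcomes:

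> With 187 patients per arm and an unadjusted two-sided 5% level, the trial has 80% power for a pairwise difference from placebo of 13.6 percentage points in one-year mortality (control 40%), 14.3 points (control 50%), or 2.2 days of ICU stay (SD 7.6). These are two-proportion and two-mean approximations; the planned analyses are time-to-event.

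If 2.5% is kept as a conservative pairwise level, give 14.9 points, 15.7 points and 2.43 days in both documents, and say that the secondary tests themselves are run at 5%. Because the SAP heading attributes the section to the grant, add a line saying that this paragraph supersedes the grant's figures.

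The cost is wording only. At 5% the SAP's detectable differences become slightly less favourable (13 to 13.6 points, 14 to 14.3 points, 2 to 2.2 days). The sample size and every planned test stay the same.

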7.7 The Vanderbilt Coordinating Center (VCC). The VCC has extensive experience in the conduct of large, phase III clinical trials over the past decade and is comprised of over 50 people on-site at Vanderbilt. The VCC will perform (among other functions) the following: communicate with the FDA using a schedule of reporting in accordance with IND policies, design the database and data collection tool, establish a web-based data database, conduct startup meetings and site-training regarding protocol implementation and delirium monitoring to standardize all research activities during the trial, monitor enrollment pace and quality to ensure patients meet the inclusion/exclusion criteria, maintain blinding, track adverse events and ensure safety reporting, ensure protocol compliance, store plasma, serum, and genetic samples for planned and future analyses, conduct follow-up phone testing of neuropsychological function and quality of life via neuropsychology technicians, and work with the study centers and local study personnel using multiple proven patient retention techniques that have consistently achieved over 80% follow-up during previous studies.

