# 9.0 Reporting of Adverse Events or Unanticipated Problems involving Risk to Participants or Others

A system has been established to report and track clinical outcomes and adverse events (AEs). Study personnel will monitor the safety of subjects and follow them until the event resolves or is explained.

**9.1** Clinical Outcomes (not considered Adverse Events). In this study of critically ill patients who are at high risk for death or other adverse outcomes due to their underlying critical illness, clinical outcomes, including death and organ dysfunction, will be systematically tracked (collected in the CRF) and will be included as part of the safety and efficacy analyses for this study. For the purposes of reporting, death and organ dysfunction will not be recorded as adverse

MIND-USA Protocol Version: 1.15 Confidential Protocol Date: June 22, 2016 29 of 51

events unless the investigator believes the event may have been caused by study drug and is more severe or prolonged than expected given the underlying critical illness (investigator's discretion). This approach—considering death and organ dysfunction as outcomes rather than adverse events and systemically tracking expected safety outcomes for analysis rather than solely recording individual adverse events—is common in ICU trials because these outcomes/events occur commonly in the ICU and this system mandates that data regarding death, organ dysfunction, and expected safety outcomes be tracked systematically for all patients and analyzed appropriately. All clinical outcomes will be systemically tracked throughout the Treatment Period and the Post-Study Drug Period as described in section 7.3.2. Listed below are events that will be tracked as clinical outcomes and will not therefore be required to be reported as adverse events during this study (unless believed to be study-drug related and more severe or prolonged than expected given the underlying critical illness):

- [1] Death. All deaths occurring within the Interventional Trial Phase will be reported on the CRF in the death summary section. For deaths thought to be caused by study drug, a SUSAR (see section 9.2) will be reported along with the death summary.
- [2] Respiratory failure, including need for mechanical ventilation (invasive or noninvasive) or episodes of hypoxemia
- [3] Circulatory failure, including shock (whether requiring vasopressors or not) and cardiac arrhythmias, and hypertension

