- [4] Hepatic failure or injury leading to increased bilirubin
- [5] Renal failure or injury leading to an increased creatinine or acute hemodialysis
- [6] Coagulation derangements leading to thrombocytopenia
- [7] Stroke and neuropsychological dysfunction that is believed to be newly acquired
- [8] Alterations in vital signs (e.g., temperature, respiratory rate, oxygen saturation)
- [9] Thromboembolisms
- [10] ICU readmissions
- [11] Infections
- [12] Self-removal of devices and invasive tubing and/or monitoring equipment
- [13] The following known adverse reactions to antipsychotics:
  - (a) NMS
  - (b) acute dystonia (i.e., muscle spasms and contractions)
  - (c) pseudoparkinsonism
  - (d) atrial and ventricular dysrhythmias
  - (e) hyperglycemia
  - (f) extrapyramidal symptoms (EPS)
  - (g) tardive dyskinesia
  - (h) akathisia
  - (i) QTc prolongation  $\geq$  550 ms
- 9.2 Adverse Events (AEs), Serious Adverse Events (SAEs), and Serious Unexpected Suspected Adverse Reactions (SUSARs). An Adverse Event (AE) will be any untoward medical occurrence for a patient enrolled in the trial that is not tracked as a clinical outcome (see section 9.1), regardless of whether the event is considered study drug-related or not. If a subject experiences an AE after informed consent is signed but before receiving study drug, the event will be reported as an AE not study drug related. Prior to enrollment, study site personnel will note the occurrence and nature of each subject's medical condition(s). During the study, site

MIND-USA Protocol Version: 1.15 Confidential Protocol Date: June 22, 2016 30 of 51

personnel will note changes in these condition(s) and/or the occurrence and nature of any AEs. All AEs occurring during the Treatment Period and/or the Post-Study Drug Period will be recorded on the CRF. This period is the window of time during which study drug-related adverse reactions are expected based on the duration of the study drug administration plus 4 additional days of Post-Study Drug Period (approximately 4-5 elimination half-lives of haloperidol, the longer acting of the two active study drugs). An AE that later meets criteria for an SUSAR between the start of study drug and hospital discharge will be reported as an SUSAR. If study drug is discontinued as a result of an AE, study personnel will document the circumstances leading to discontinuation of study drug.

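### The SAP promises that the follow-up team is blinded to the hospital course, but its access table opens the in-hospital adverse-event and notes-to-file forms to that team

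*SAP*

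**What the plan says.** The passage is step 3a of the SAP's In-Hospital Database Cleaning & Lock Procedures, which sets permissions for the In-Hospital Database while long-term follow-up is still running. It makes three statements about the Follow-Up Team.

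- **Blinding sentence.** "The follow-up team will continue to be blinded (via restricted access) to all information about the hospital course". It adds that this has been so throughout the study.
- **Narrative access rule.** "VCC Project Managers and the Follow-Up Team will be restricted to read-only access for all fields except those needed for patient contact", followed by further exceptions that include notes to file, event reporting, and dates of death and withdrawal.
- **Access table, Follow-Up Team column.** View and Edit for the Contact Form, for "Adverse Events - all fields", for "NTF - all fields", and for the row "Dates Tracking Form - all variables made read-only (using action tag @readonly) to all users except variables pertaining to consenting, death and study withdrawal". No Access for the DNA Log and for all other forms and fields.

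The protocol says what the adverse-event record holds. Section 9.2: "All AEs occurring during the Treatment Period and/or the Post-Study Drug Period will be recorded on the CRF". The same section also has events between consent and first dose reported, as not drug-related. Every adverse event is judged for relatedness, seriousness and expectedness, and section 9.3 places the record in the electronic database. Under section 9.1, the known antipsychotic reactions are tracked as clinical outcomes and need not be reported as adverse events "unless believed to be study-drug related and more severe or prolonged than expected given the underlying critical illness".

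On who does the telephone testing, Protocol 7.7 says the coordinating center will "conduct follow-up phone testing of neuropsychological function and quality of life via neuropsychology technicians".

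**The concern.** The blinding sentence covers the whole hospital course and names restricted access as its mechanism. The table that sets the access then opens two in-hospital forms in full. One of them records events that an investigator has judged for a link to study drug.

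At stake is the masking of the assessors for Aim 4: cognition (SO8), function and quality of life (SO9) and PTSD symptoms (SO10), all obtained by telephone at 3 and 12 months. An assessor who has read that a patient had a suspected reaction to study drug has some basis for guessing active treatment. Even without a guess about arm, knowing about a complicated hospital stay may colour how an interview is conducted. The sponsor evidently thought this worth guarding against, since the SAP claims the protection. A trial report that repeats the claim should be able to rely on it.

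**Working it through.** No arithmetic applies to the contradiction itself. It is settled by setting the passages side by side.

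**1. Promise against permissions (SAP step 3a)**

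| Form in the In-Hospital Database | Follow-Up Team access in table | Consistent with blinding to the hospital course? |
|---|---|---|
| Contact Form | View and Edit | Yes, on its face |
| Dates Tracking Form | View and Edit; variables other than consent, death and withdrawal are read-only | Unclear: read-only fields remain visible, and the form's contents are not listed |
| Notes to file | View and Edit, all fields | No, if any note concerns the hospital stay; contents are not described |
| Adverse Events | View and Edit, all fields | No |
| DNA Log | No Access | Yes |
| All other forms and fields | No Access | Yes |

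Four of six rows are open and two are closed. The adverse-event row is the clear conflict. The notes-to-file row conflicts on its wording, and the dates row needs checking.

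**2. Is the adverse-event form hospital-course information?** Yes. Recording covers the Treatment and Post-Study Drug Periods, and Protocol 7.5 limits daily data to 18 days or until discharge or death. Events between consent and first dose are added. All of this precedes the 3-month call.

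**3. Does it carry information about study drug?** In part. All adverse events are entered whether or not they are thought related, so drug-attributed events are a subset. Relatedness is assessed for each one. Under 9.1, an antipsychotic-type reaction on this form is likely to be one that an investigator attributed to study drug and found worse than expected. The same rule keeps most such reactions off the form, so revealing entries should be few.

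**4. Is there a mask elsewhere?** Neither document describes a field-level or record-level mask on in-hospital adverse events or notes for this team.

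**5. Narrative against table.** The narrative puts project managers and the Follow-Up Team under one rule: read-only for whatever is not excepted. The table's last row gives project managers Read Only, which matches, but gives the Follow-Up Team No Access, which does not. The table is the more specific statement and agrees with the blinding sentence, so the narrative is probably the slip. Both still stand in the SAP.

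**6. Are these the outcome assessors?** No sentence equates the Follow-Up Team with the SO8 to SO10 assessors. Protocol 7.4 has trained study personnel do the testing under the coordinating center's lead neuropsychologist, and 7.7 assigns it to the center's technicians. There would be little reason to blind the team to the hospital course if it did not assess outcomes. The identity is very probable but inferred.

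**The case against.** **The access has an operational purpose.** Step 3a lists event reporting and notes to file among the tasks for which edit rights are kept. That stands as a reason to enter new events. It does not explain sight of existing in-hospital entries.

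**Assignment stays masked.** Protocol 6.2 restricts the randomization lists to investigational pharmacists, and 6.3 keeps study personnel blinded through follow-up and analysis. Relatedness is judged by blinded investigators, so placebo patients can also carry a related label. This stands: an entry supports a guess about arm and no more. The SAP's promise, however, is wider than assignment.

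**Room for assessor influence is limited.** SO8 uses standard tests with standard scoring, SO10 is a checklist and SO9 is largely questionnaires. This stands, and it is one reason to expect a small effect.

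**Details may sit in the Database Cleaning & Lock SOP**, which is not part of these documents. That is possible. The SAP's own sentence and table would still disagree.

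Three stronger readings are tempting and are not supported:

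- *That the whole in-hospital record is open to the team.* The narrative taken alone could suggest this, but the table's last row gives No Access to all other forms and fields.
- *That the notes to file or dates form reveal study drug.* The contents of neither form are described.
- *That a one-directional bias can be quantified.* Protocol 11.3 plans 561 x 0.69 x 0.80 = 310 tested at 12 months, about 310/3 = 103.3 per arm, so the standard error of a standardised difference between two arms is sqrt(2/103.3) = 0.139 SD. If 5% to 20% of active-arm patients and no placebo patients had a revealing entry, and each shifted a score by 0.2 to 0.5 SD, the bias would run from 0.05 x 0.2 = 0.01 SD to 0.20 x 0.5 = 0.10 SD, or 0.07 to 0.72 of a standard error. Neither input comes from the documents. The zero share in placebo sits badly with the pilot in Protocol 3.3, which saw no between-group difference in the anticipated drug-related events, and with the one QTc prolongation in each group in 3.2. With equal shares and equal shifts the differential bias is zero. Direction is open too, because the protocol argues equipoise between benefit and harm.

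**Conclusion.** The contradiction is real and can be read directly from step 3a: blinding to the hospital course is claimed through restricted access, and the access table does not deliver it for the Adverse Events form or, on its wording, for notes to file. The read-only sentence is a second, smaller inconsistency with the same table.

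The consequence is limited. It touches SO8 to SO10, provided the Follow-Up Team conducts those calls, which is very probable but not stated. It does not touch delirium/coma-free days, and it does not expose the assigned arm. The size and direction of any bias cannot be estimated, because the documents give no adverse-event rates for this trial and no basis for a shift in scores. Few revealing entries and largely standardised instruments suggest that it is small. The correction is still worth making: it is cheap, and without it the report would claim assessor blinding that the plan does not provide.

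**What to change.** 1. In the step 3a table, set the Follow-Up Team to No Access on the Adverse Events form and on in-hospital notes to file, or hide the existing in-hospital entries from that team.
2. Have events learned at follow-up calls entered on a separate follow-up event form.
3. Remove the Follow-Up Team from the read-only sentence so that it matches the table's No Access row.
4. Confirm that the Dates Tracking fields visible to the team reveal nothing about the hospital course, and hide any that do. The read-only tag prevents editing, not viewing.
5. State in the SAP whether the Follow-Up Team conducts the SO8 to SO10 assessments.
6. Establish what access the team had before the lock. If it could already see these forms, say so in the SAP and the report instead of claiming full blinding to the hospital course.

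The cost is a database permission change, one short form and a few SAP sentences. The small downside is that follow-up events sit on a form of their own.
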